9.3 Pregnancies

[figure not shown]
Pregnancy, in and of itself, is not regarded as an AE, unless there is suspicion that study drug may have interfered with the effectiveness of a contraceptive medication or method.

To ensure patient safety, each pregnancy in a patient on study treatment must be reported to Novartis within 24 hours of learning of its occurrence. The pregnancy should be followed up to determine outcome, including spontaneous or voluntary termination, details of the birth, and the presence or absence of any birth defects, congenital abnormalities, or maternal and/or newborn complications. Pregnancy outcomes must be collected for the female partners of any males who took study treatment in this study. Consent to report information regarding these pregnancy outcomes should be obtained from the mother.

Pregnancy should be recorded on a Clinical Study Pregnancy Form and reported by the investigator to the oncology Novartis Drug Safety and Epidemiology (DS&E) department. Pregnancy follow-up should be recorded on the same form and should include an assessment of the possible relationship to the Novartis study treatment of any pregnancy outcome. Any SAE experienced during pregnancy must be reported on the SAE Report Form.

The procedures that will be followed based on whether a pregnancy is confirmed by a positive serum or urine test result are listed below:

- Investigator and subject must notify each other immediately.
- Investigator must notify the Sponsor immediately.
- Discontinue study drug immediately.
- Perform the required End-of-treatment visit study evaluations.

- Investigator must complete and submit the Pregnancy Initial and Follow-up report forms to the Sponsor.
- A serum pregnancy test must be performed to confirm the urine test result. (The serum test should be performed at the investigative site to ensure the test will be performed promptly and the result available immediately for review.)
- Withdraw the patient from the study.

If a negative serum test does not confirm the urine test result, then:

- The investigator will use his/her expert judgment, based on an assessment of the potential benefit/risk to the subject, to determine if it is in the patients best interest to resume study drug and continue participation in the study.

Any pregnancy diagnosed during the study, or that occurs within 28 days after stopping study drug, must be reported immediately to the investigator. The investigator will notify the Sponsor or designee by following the procedures described in [Section 9.2.2](#). The outcome of all such pregnancies (i.e., spontaneous miscarriage, elective termination, normal birth, or congenital abnormality) must be documented and followed-up on a form that will be provided by the Sponsor. The pregnancy will be followed to term and the outcome, including any premature termination, must be reported to the Sponsor. All live births must be followed for a minimum of 30 days or to the first well-baby visit. All reports of congenital abnormalities/birth defects and spontaneous abortions/miscarriages should be reported as an SAE for this study. Elective abortion procedures, without complications, should not be considered as AEs.

9.4 Warning and precautions

No evidence available at the time of the approval of this study protocol indicated that special warnings or precautions were appropriate, other than those noted in the provided [Investigator Brochure]. Additional safety information collected between IB updates will be communicated in the form of Investigator notifications. This information will be included in the patient informed consent and should be discussed with the patient during the study as needed.

[figure not shown]
10 Data collection and management

10.1 Data confidentiality

Information about study subjects will be kept confidential and managed under the applicable laws and regulations. Those regulations require a signed subject authorization informing the subject of the following:

- What protected health information (PHI) will be collected from subjects in this study.
- Who will have access to that information and why.
- Who will use or disclose that information.
- The rights of a research subject to revoke their authorization for use of their PHI.

In the event that a subject revokes authorization to collect or use PHI, the investigator, by regulation, retains the ability to use all information collected prior to the revocation of subject

authorization. For subjects that have revoked authorization to collect or use PHI, attempts should be made to obtain permission to collect at least vital status (i.e. that the subject is alive) at the end of their scheduled study period.

The data collection system for this study uses built-in security features to encrypt all data for transmission in both directions, preventing unauthorized access to confidential participant information. Access to the system will be controlled by a sequence of individually assigned user identification codes and passwords, made available only to authorized personnel who have completed prerequisite training.

Prior to entering key sensitive personally identifiable information (Subject Initials and exact Date of Birth), the system will prompt site to verify that this data is allowed to be collected. If the site indicates that country rules or ethics committee standards do not permit collection of these items, the system will not solicit Subject Initials. Year of birth will be solicited (in the place of exact date of birth) to establish that the subject satisfies protocol age requirements and to enable appropriate age-related normal ranges to be used in assessing laboratory test results.

10.2 Site monitoring

Before study initiation, at a site initiation visit or at an investigator's meeting, a Novartis representative or authorized designee will review the protocol and eCRFs with the investigators and their staff. During the study, the field monitor will visit the site regularly to check the completeness of patient records, the accuracy of entries on eCRFs, the adherence to the protocol and to Good Clinical Practice, the progress of enrollment, and to ensure that study drug is being stored, dispensed, and accounted for according to specifications. Key study personnel must be available to assist the field monitor during these visits.

The investigator must maintain source documents for each patient in the study, consisting of case and visit notes (hospital or clinic medical records) containing demographic and medical information, laboratory data, electrocardiograms, and the results of any other tests or assessments. All information on eCRFs must be traceable to these source documents in the patient's file. Data not requiring a separate written record will be defined before study start and will be recorded directly on the eCRFs, which will be documented as being the source data (see items listed as Category "D" in [Table 7-1](#) and [Table 7-2](#)). The investigator must also keep the original informed consent form signed by the patient (a signed copy is given to the patient).

The investigator must give the monitor access to all relevant source documents to confirm their consistency with the eCRF entries. Novartis monitoring standards require full verification for the presence of informed consent, adherence to the inclusion/exclusion criteria, documentation of SAEs, and the recording of data that will be used for all primary and safety variables. Additional checks of the consistency of the source data with the eCRFs are performed according to the study-specific monitoring plan. No information in source documents about the identity of the patients will be disclosed.

10.3 Data collection

The designated investigator staff will enter the data required by the protocol into the eCRF using fully validated software that conforms to 21 CFR Part 11 requirements. Designated investigator site staff will not be given access to the EDC system until they have been trained. The Principal Investigator is responsible for assuring that the data entered into the eCRF is complete, accurate, and that entry is performed in a timely manner. Automatic validation programs check for data discrepancies in the eCRFs and, by generating appropriate error messages, allow modification or verification of the entered data by the investigator staff before transfer to Novartis (or designated CRO) via a secure network. After database lock, the investigator will receive a CD-ROM or paper copies of the patient data for archiving at the investigational site.

In addition, data collected will include:

- information about previous fedratinib treatment and the end date,
- for those patients with fedratinib treatment:
 - information about ruxolitinib received or not,
 - and if ruxolitinib received, information on receipt when participating to CINC424A2401 or not will be collected. For patient enrolled previously in CINC424A2401, previous patient number will be collected.

[figure not shown]
10.4 Database management and quality control

Data will be entered into the study database by Investigator/Study Coordinator for electronic data capture (EDC) studies.

Novartis personnel (or designated CRO) will review the data entered by investigational staff for completeness and accuracy. Detected discrepancies for which the resolution is obvious/self-evident will be corrected by Novartis Data Management personnel (or designated CRO). Electronic data queries are stating the nature of the problem and requesting clarification will be created for all other discrepancies and missing values and sent to the investigational site via the EDC system. Designated investigator site staff is required to respond promptly to queries and to make any necessary changes to the data.

Concomitant treatments entered into the database will be coded using the WHO Drug Reference List, which employs the Anatomical Therapeutic Chemical classification system. Medical history/current medical conditions and adverse events will be coded using the Medical dictionary for regulatory activities (MedDRA) terminology.

At the conclusion of the study the occurrence of any protocol deviations will be determined. After these actions have been completed and the database has been declared to be complete and accurate, it will be locked and made available for data analysis. Any changes to the database after that time can only be made by joint written agreement between the Global Head of Biostatistics and Statistical Reporting and the Global Therapeutic Area Head.

11 Statistical methods and data analysis

The primary objective of this study is to collect safety data on patients with PMF, PPV MF, or PET-MF treated by INC424, while secondary objectives are on collecting some efficacy data and medical resource use.

This section is describing all analyses to be performed, the primary and secondary objective being descriptive; no hypotheses testing will be performed.

The data will be analyzed by Novartis. All data from all centers that participate in this protocol will be combined and analyzed together.

Timing of analyses

The primary analysis will be performed after all patients have either completed 24 months of treatment or have been prematurely discontinued from the study. All patients should have been followed for 28 days after they have discontinued INC424, data collected during this follow-up period will be included in the analysis. An interim analysis planned for this study will take place when 50 patients with low platelets will have completed 6 months of treatment.

Additional analyses may also be performed if needed to fulfill regulatory obligation or publication purpose.

Statistical reporting and grouping

Data will be analyzed according to platelet count at baseline and displayed considering the following two groups:

- Low platelet patients (platelets < 100, 000 / μ L)
- and non-low platelets (platelets \geq 100, 000 / μ L).

[figure not shown]
All analyses for categorical data will be presented as frequencies and percentages (% based on number of patients from the considered population unless specified otherwise).

For all continuous data, except time related ones, the following descriptive statistics will be presented: n, mean, standard deviation, median, minimum and maximum. Time related data (i.e. durations such as overall survival) will be summarized using n, median, minimum and maximum.

For all analyses, **baseline value** will be defined as the latest available assessment obtained prior to the date of first dose of study drug administration. If assessment prior to first dose of study drug administration is not available, then assessment on the day of first dose of study drug administration will be used at baseline.

All data considered in the analysis will be listed individually.

Please note: due to the trial design and intent, it is not possible to ensure that a sufficient number of patients will be available to conduct the analyses as planned. Therefore, it is important to consider that certain analyses described in the subsequent section may not be relevant if study population is too small.

11.1 Handling of missing values

No imputation for missing data will be performed, unless otherwise specified

11.2 Populations for analysis

Full Analysis Set (FAS) consists of all patients who received at least one administration of study drug.

Safety set consists of all patients who received at least one dose of study drug and had at least one post-baseline safety assessment.

Please note: the statement that a patient had no adverse events (on the Adverse Event CRF) constitutes a safety assessment. Patients who have received at least one dose of study drug but who have no post-treatment safety data of any kind would be excluded from the safety population.

Per protocol set: Consists of all FAS patients without any major protocol deviation. Rules for identifying major protocol deviations will be detailed in RAP.

11.3 Patient demographics/other baseline characteristics

Demographic (gender, age, weight, height, BMI) and other baseline data (disease characteristics, medical history, medication history, and serology) will be summarized descriptively for all patients of the FAS.

11.4 Treatments (study drug, concomitant therapies, compliance)

All analyses from this section will be performed on all patients from the safety set.

Duration of INC424 administration will be summarized using descriptive statistics. Also, proportion of patients by dose intensity range will be presented.

Frequency of dose reductions and interruptions will be summarized by reason, if available. The duration of the dose interruptions will also be summarized.

Concomitant medications and significant non-drug therapies prior to and after the start of the study drug will be summarized by ATC code.

11.5 Primary objective

[figure not shown]
The primary objective of this study is to collect safety data on patients with PMF, PPV MF, or PET-MF treated by INC424. This will be assessed considering incidence of treatment-emergent AEs.

The safety set will be used for the analysis of clinical safety data.

11.5.1 Variables

Primary analysis will be performed on the **incidence of treatment-emergent AEs**.

Incidence of a given AE is defined as the ratio of total number of patients experiencing at least once this AE (defined by its preferred term) divided by the total number of patients in the safety set.

A treatment-emergent AE is an AE that starts during treatment (including the 28 days following last treatment administration) or worsen on treatment.

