When pooling the results of COMFORT-I and COMFORT-II to examine safety of INC424, the incidence of headache was more frequent in INC424-treated patients (13.6% vs. 6.0% on placebo and 5.5% on BAT). Most AEs of headache were Grade 1 or 2. Similarly, dizziness (12.0% vs. 6.6% on placebo and 6.8% on BAT) was more frequent in INC424-treated patients, again mostly Grade 1 or 2. When adjusted for patient-year exposure, the differences were still present for headache and dizziness. Weight increase was also more frequent in INC424-treated patients than in the control groups (9.6% vs. 1.3% on placebo and 1.4% on BAT). Although some of these patients had co-reported AEs of edema, many had a past medical history of weight loss and the weight gain usually gradually accumulated over the course of one year of treatment. The majority of weight gain AEs were Grade 1 and 2. It is worth noting that weight gain may be a beneficial effect in patients with MF, given the catabolic nature of the disease and the frequency of weight loss reported as a constitutional symptom.

Other “preferred terms” with increased frequency in the INC424 arms included bruising (2.6% vs. 1.3% on placebo in [COMFORT-I, INCB 18424-351] only), contusion (8.6% vs. 5.3% on placebo and 1.4% on BAT), urinary tract infection (7.3% vs. 4.6% on placebo and 2.7% on BAT), herpes zoster (4.0% vs. 0.7% on placebo and 0% on BAT) and flatulence (3.3% vs. 1.3% on placebo and 0% on BAT). Abdominal pain was more frequent in the control groups than in the INC424 group (43% on placebo and 13.7% on BAT vs. 12% on INC424), as were weight decrease (8.6% on placebo and 8.2% on BAT vs. 1% on INC424), early satiety (8.6% on placebo and 0% on BAT vs. 0.3% on INC424) and splenic infarction (6.0% on placebo and 0% on BAT vs. 1.0% on INC424).

The most frequently occurring Grade 3 and 4 AEs regardless of study drug relationship were hematologic including anemia (14%) and thrombocytopenia (8%) (Source: [120 day safety update-Table 2.1-1.4 in Investigator Brochure]). Non-hematologic Grade 3-4 AEs were infrequent and rarely reported more frequently than in the control arms. Two patients (0.7%) had febrile neutropenia. In general, the pattern of AEs was similar between the two INC424 arms in both studies, although there were some differences in frequency for specific AEs.

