4.1 Description of study design

This is a multicenter, single-arm, open-label expanded access study intended to provide additional data on the safety and efficacy of INC424 in patients with PMF, PPV MF, or PET-MF who have either previously received treatment or have not received treatment.

[figure not shown]

All patients will be treated for PMF, PPV MF, or PET-MF in each participating country with oral INC424 at a dose of 5 - 25 mg (dose based on Baseline platelet count) BID until either:

- Disease progression;
- Transplant;
- Unacceptable toxicity;
- Death;
- Discontinuation from the study for any other reason;
- Physician decision;
- Withdrawal of consent;
- Until 24-months after LPFV; or
- Until the drug is commercially available, whichever occurs first.

The FPFV occurred on 16 August 2011 and the recruitment period ended on December 31, 2014. The study enrolled a total of 2238 patients. The last patient last visit is planned for Dec 2016.

Figure 4-1 Study design

* Baseline evaluations should be performed within 7 days of the first dose of INC424, however platelets should be performed within a maximum of 4 days of the first dose of INC424

All patients should be screened for inclusion and exclusion criteria (Section 5.2 and Section 5.3) within 28 days prior to the first dose of INC424. See Section 7.3 for a description of the required screening evaluations. Baseline evaluations should be performed within 7 days of the first dose of INC424, however platelets should be performed within a maximum of 4 days of the first dose of INC424. See Section 7.4 for a description of the baseline evaluations required.

Screening and eligibility: Eligibility assessment may take place up to 28 days before the first dose of INC424 (Day -28 to Day -1). See Section 7.3 for required assessments.

To avoid duplication of laboratory assessments and other examinations during the 28 days before Day 1, it is permissible to use historical results provided the examinations were performed consistent with protocol requirements 7 days prior to date of first dose, however platelets should be performed within a maximum of 4 days of the first dose of INC424.

Rescreening of patients is permissible at the discretion of the investigator i.e., a patient is screened and is found to be ineligible, they may be rescreened at a later date and entered onto the study provided **all** inclusion and **no** exclusion criteria are met. Rescreening should not occur more often than every 7 days.

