3.4.1 Primary endpoints

3.4.1.1 Variables

The analysis of the primary endpoint will be performed on the incidence by patients of **treatment-emergent AEs** considering or not certain AEs characteristics (e.g. relationship to study medication, severity).

Incidence of a given AE is defined as the ratio of total number of patients experiencing the given AE at least once (defined by its preferred term [PT]) divided by the total number of patients at risk (i.e. part of the safety set).

A treatment-emergent AE is an AE that first occurs or worsens during treatment (including the 28 days following last treatment administration).

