3.5 Safety evaluation

This section describes the planned statistical analyses for Sections 10, 12, 14, and 16 of the clinical study report.

Safety analysis will be based on safety population and will use the data collected during the study. Cut off for the safety reporting is end-of-treatment date + 28 days.

The following safety endpoints will be analyzed:

- Treatment-emergent AEs and serious adverse events (SAEs).
- AEs leading to study drug discontinuation.
- Adverse events of interest.
- Clinical laboratory values.
- Vital signs.
- Targeted physical examinations.
- 12-lead electrocardiograms (ECGs).

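### The primary AE incidence is a crude proportion with no common time base, and no exposure-based or fixed-time AE estimate is planned beside it

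*Protocol*

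**What the plan says.** Protocol 11.5.1 makes the incidence of treatment-emergent AEs the primary variable. For each preferred term it is the number of patients with at least one event "divided by the total number of patients in the safety set". SAP 3.4.1.1 repeats the ratio, "divided by the total number of patients at risk (i.e. part of the safety set", so being at risk means only being in the safety set. Entry to that set requires that the patient "received at least one dose of study drug and had at least one post-baseline safety assessment" (Protocol 11.2).

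The event window belongs to the individual patient. It is the treatment period, "including the 28 days following last treatment administration" (Protocol 11.5.1), and SAP 3.5 agrees: "Cut off for the safety reporting is end-of-treatment date + 28 days". Treatment ends for clinical reasons or administratively, at 24 months after last patient first visit or "Until the drug is commercially available, whichever occurs first" (Protocol 4.1). The synopsis adds that the trial may stop in one country ahead of others.

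Protocol section 11 times the primary analysis for when every patient has completed 24 months or stopped early. That sets the analysis date; it does not cap the AE window at 24 months. SAP 3.2 summarises duration of exposure and follow-up, including by duration category, but does not link them to AEs. Protocol 11.5 and SAP 3.4.1 and 3.5.1 contain no patient-year rate, time-to-first-AE analysis, cumulative incidence or AE table by fixed time window.

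**The concern.** For any event that keeps accruing, a crude proportion rises with the length of observation. Protocol 1.3.5 says as much about earlier studies: with longer follow-up, the proportions of patients with AEs and SAEs went up. Here the length of observation is set partly by things unrelated to the drug's safety, namely when the patient enrolled and when the drug reached the market in that country. The second is not hypothetical. European approval came on 31 August 2012, about a year into a recruitment period of more than three years, and Protocol 1.3 reports approval in over 90 countries.

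Collecting safety data is the study's primary objective. A pooled percentage without a time base does not tell a reader what risk to expect by six months or a year on treatment, and a long study should be well placed to answer that. The plan also displays results by baseline platelet group (Protocol section 11) and uses the non-low group as an internal reference at the interim analysis (Protocol 11.7, SAP 3.7). Neither text says how differing exposure is handled there.

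**Working it through.** The plan has no sample-size or precision figure to reproduce, so the check is calendar arithmetic followed by an illustration.

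**Calendar inputs (Protocol 4.1).** "The FPFV occurred on 16 August 2011 and the recruitment period ended on December 31, 2014". Last patient last visit is planned for December 2016.

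- Longest possible exposure: 16 August 2011 to 31 December 2016 = 1,964 days; 1,964 / 365.25 = 5.38 years (5.30 if the end is 1 December).
- Patient enrolled on 31 December 2014: at most 2.0 years.
- Shortest: one dose plus one post-baseline safety assessment, so days are possible.
- Low-platelet patients: assuming that none entered before the date of Amendment 2, 13 August 2012, at most 4.38 years.

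These are limits implied by dates and eligibility. The documents give no observed exposure distribution.

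**By length of exposure.** Assume a constant hazard λ = 0.10 per patient-year. Crude incidence = 1 − exp(−λ × (t + 28/365.25)).

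| Exposure t | Crude incidence |
|---|---|
| 14 days | 1.1% |
| 3 months | 3.2% |
| 1 year | 10.2% |
| 2 years | 18.8% |
| 5.38 years | 42.0% |

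**For the whole study.** The study reports a mixture of exposures, so the relevant quantity is the pooled figure. Assumptions, none from the documents: uniform accrual over the recruitment period, administrative stop on 31 December 2016, exponential discontinuation, and exponential time from first dose to commercial availability. Each scenario simulates 400,000 patients with λ = 0.10.

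| Discontinuation per year | Mean time to availability | Median exposure (years) | Crude incidence | First events per 100 patient-years |
|---|---|---|---|---|
| 0.1 | never | 3.08 | 26.0% | 9.92 |
| 0.1 | 2 years | 1.15 | 13.6% | 10.00 |
| 0.1 | 1 year | 0.63 | 8.8% | 9.99 |
| 0.3 | never | 2.15 | 19.4% | 9.98 |
| 0.3 | 2 years | 0.87 | 11.2% | 9.97 |
| 0.3 | 1 year | 0.53 | 7.7% | 9.93 |
| 0.6 | never | 1.15 | 13.6% | 9.98 |
| 0.6 | 2 years | 0.63 | 8.8% | 9.94 |
| 0.6 | 1 year | 0.43 | 6.5% | 9.97 |

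The 12-month cumulative incidence is 1 − exp(−0.10) = 9.5% in every row. The crude figure spans 26.0 / 6.5 = 4-fold with the same underlying risk. At λ = 0.05 the crude range is 3.4% to 14.3%; at λ = 0.20 it is 12.4% to 44.4%.

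**Platelet groups, accrual timing alone.** Same λ = 0.10 in both groups, no commercial cut-off, low-platelet entry from 13 August 2012: 26.2% non-low against 24.0% low with discontinuation 0.1 per year, and 19.5% against 18.4% with 0.3 per year. The gap is about 1 to 2 points.

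**Early-onset events.** Protocol 1.3.5 says that about half of the Grade 3/4 anemia and thrombocytopenia events in COMFORT-I fell in the first 8 weeks. Take an assumed hazard of 1.0 per year for 8 weeks (0.153 years), then 0.05 per year, and leave out the 28-day tail.

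- Cumulative hazard at 3 months: 0.153 + 0.05 × 0.097 = 0.158, so crude incidence is 14.6%.
- Cumulative hazard at 2 years: 0.153 + 0.05 × 1.847 = 0.246, so crude incidence is 21.8%, a 1.5-fold change.
- The first-event rate over the same two spans falls from 65 to 13 per 100 patient-years, a 5-fold change.

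For such events the patient-year rate depends on exposure more than the crude proportion does. Cumulative incidence at a fixed time avoids the problem.

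**The case against.** A crude treatment-emergent proportion is a usual descriptive safety summary. The study is single-arm, with no hypotheses and no power calculation, so no error rate is at stake. Exposure is tabulated in bands, all analysed data are listed, and further analyses are allowed for regulatory or publication purposes. All of this stands. It makes the gap a missing companion estimate, not a wrong formula. Banded exposure shown separately still does not let a reader recover risk by a given time.

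Several stronger readings are tempting, and the documents do not support them.

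- A reader might infer that the window is undefined. It is defined for each patient; what is missing is a common length.
- A reader might infer that the protocol relies on exposure adjustment for the Phase III data. Its background gives percentages of patients and adds one sentence: "When adjusted for patient-year exposure, the differences were still present for headache and dizziness". The planned percentages have the same format as those figures, so comparison calls for caution about follow-up but is not ruled out.
- A reader might set 3 months against 5.3 years at 0.2 per year (4.9% against 65.4% without the 28-day tail) and report a 13-fold spread. That contrasts two individual extremes. At study level the spread at the same hazard is 44.4 / 12.4, about 3.6-fold.
- A reader might infer that the platelet groups cannot be compared. Accrual timing alone shifts the contrast by about 1 to 2 points. A difference in commercial cut-off between the groups could add to this, but the documents give no figures on it.
- The number of patients moved early to commercial supply is not given, so any understatement of late events for that reason cannot be sized.

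**Conclusion.** The point holds as a worthwhile, low-cost improvement. The primary incidence has no common time base, and neither document plans an estimate that supplies one. In the illustration the pooled figure moves about 4-fold (6.5% to 26.0% at 0.10 per patient-year) on discontinuation and launch timing alone. That size rests on an assumed constant hazard and on assumed discontinuation and availability times; the documents supply only the calendar limits. The effect matters most for late or steadily accruing events and is smaller for early cytopenias. It does not invalidate the crude table.

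**What to change.** Keep the crude table and add to SAP 3.4.1:

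- **(a)** Cumulative incidence of first event at fixed times, such as weeks 24 and 48, for the main AEs, grade 3-4 AEs and SAEs. Treat a stop at commercial availability or study end as administrative censoring and death as a competing event. State also how stops for other reasons are handled, since censoring them assumes that they are unrelated to AE risk.
- **(b)** First-event rates per 100 patient-years with 95% CI, with time counted to first event or last dose plus 28 days. Note that these assume a roughly constant hazard and should be read beside (a) for early-onset events.

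Show both overall and by the baseline platelet groups of Protocol section 11, including at the interim analysis. SAP 2.2 says that no subgroup analyses are planned, so the display by platelet group has to be written in.

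The cost is a few extra tables. AE onset dates and first and last dose dates are already collected, and SAP 3.2 already derives exposure. The reason for stopping treatment is recorded too; the team should confirm that it identifies stops at commercial availability.
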